4.2.1.3 Handling missing data for the other efficacy endpoints

For other binary efficacy endpoints, missing data will be imputed using the same method as the primary efficacy endpoint. NRI and OC methods will be performed as sensitivity analyses of HiSCR₅₀, HiSCR₇₅, HiSCR₉₀, and HiSCR₁₀₀.

For other continuous efficacy endpoints, the MI-MCMC/monotone regression method will be used to impute missing data as the primary method, regardless of whether the missing data are preceded by an intercurrent event. That is, if an intercurrent event occurs on or before a visit, the result for that visit will be treated as missing and imputed with the missing data. If the imputation model cannot converge, LOCF will be used.

For other ordinal endpoints (EQ-5D-3L, PGI-S-HS, PGI-C-HS, PGI-S-SP, PGI-C-SP), the OC method will be applied as the primary analysis method. No imputation is applied.

4.2.1.4 Missing Data Overview and Summary

In summary, the approaches listed below will be used in this study for handling missing data for efficacy endpoints as appropriate:

- **NRI:** Participants who have missing data at the timepoint of interest are treated as though they did not respond to the treatment. This approach is also referred to as Composite Estimand (NRI).
- **Multiple Imputation (MI) – MCMC / Monotone Regression:** Using multiple imputation methodology, intermittent missing data are imputed based on the MCMC method, and monotone missing data are imputed using monotone regression.
- **MI–MCMC / Reference-based imputation:** Using multiple imputation methodology, intermittent missing data are imputed based on the MCMC method, and monotone missing data are imputed using an imputation model based on placebo (reference) data.
- **LOCF:** Post-Baseline missing data are imputed by carrying forward the last available observation (including Baseline).
- **Tipping point analyses:** Assumptions will be made about average outcomes among the subsets of participants who prematurely discontinued study treatment. Various “delta adjustments” will be made to the assumed responses among missing data in each treatment arm with varying degrees of plausibility in order to identify assumptions about the missing

data under which the conclusions change (O’Kelly, 2014). Then, the plausibility of such assumptions is discussed.

- **Observed case (OC):** Missing data are not imputed. Only participants with available data who have not discontinued study treatment at the given timepoint are considered. Study participants with missing data or who have prematurely discontinued study treatment will be treated as missing.
- **Treatment policy strategy:** All available data observed at the time point of interest will be considered, regardless of the occurrence of intercurrent events. This means the analysis includes on- and off-treatment values collected after study participants prematurely discontinued study treatment but agreed to remain on the study and continued to attend visits and provide assessments at those visits as well as values from study participants who received rescue antibiotic medication. Those observed values will be analyzed according to the study participant’s randomized treatment. Study participants for whom efficacy data cannot be obtained at the week of interest, despite attempts to retain them in the study, will have their data imputed using MI – MCMC / monotone.

The following table depicts which missing data handling approaches will be used based on endpoint priority (primary, secondary, other) and endpoint type (responder, continuous, ordinal).

Table 4–1: Missing data handling approach by endpoint priority and type

End-point Priority	Endpoint Type	Composite Estimand (NRI)	Modified Composite Estimand (MI)	MI (MCMC/Reference-based)	Tipping Point	Treatment Policy	Hypothetical Estimand	OC
Primary	Responder	S ^a	P	S ^a	S	S ^a		S
Secondary included in the statistical testing procedure	Responder	S ^a	P					S
	Continuous						P	S
Secondary not included in statistical testing procedure	Binary	X	X					X
	Continuous						X	X
Other	Responder	X ^d	X					X ^d
	Continuous						X	X ^b
	Ordinal						X ^c	X ^c

MI=multiple imputation, NRI=Nonresponder imputation, OC=Observed case, P=Primary method, S=Sensitivity method, X=Method to be used (no priority designated).

Note: Composite estimand (NRI) refers to the approach in which data preceded by the intercurrent event of study treatment discontinuation due to AE or lack of efficacy or receipt of rescue antibiotic medication are imputed as nonresponse, and other missing data are also imputed as nonresponse.

Note: Modified Composite Estimand (MI) refers to the approach in which data preceded by the intercurrent event of study treatment discontinuation due to AE or lack of efficacy or receipt of rescue antibiotic medication are imputed as nonresponse, and other missing data are imputed via a multiple imputation model.

Note: Hypothetical Estimand (MI) refers to the approach where outcomes for study participants without an intercurrent event of study treatment discontinuation are as observed, and outcomes for study participants with the intercurrent event are imputed via a multiple imputation model.

^a Imputation method is applied on continuous data, and responder endpoint is derived from the continuous endpoint based on complete data set where applicable.

^b Required only for by-visit summaries of variables whose value at Week 16 is part of the hierarchical testing procedure.

^c For variables with multiple categories, data will be summarized as observed with an additional missing row to capture missing data at a given visit.

^d NRI/OC sensitivity analysis will be performed only for HiSCR₅₀, HiSCR₇₅, HiSCR₉₀, HiSCR₁₀₀ summaries.

4.2.2 Missing data algorithms for efficacy analyses

These descriptions focus on the missing data procedures themselves and do not specifically account for dealing with intercurrent events, which is addressed in their respective sections.

4.2.2.1 MI – MCMC / Monotone Regression

In many cases, missing efficacy data due to study treatment discontinuation should be dependent on the observed efficacy scores, but independent of unobserved data. This would be consistent with a missing at random (MAR) pattern of missingness. To investigate the efficacy results under the assumption of data being MAR, a multiple imputation method will be applied.

Binary endpoint

For a binary endpoint (eg, HiSCR₅₀), the procedure is as follows:

1. Create a data set, one for each treatment group of participants with observed values and those needing estimation by multiple imputation. For the imputation step, a distinction is made between non-monotone missing values (ie, intermittent missing values between completed assessments) and monotone missing values (ie, where all participants data are missing after a given time point).
 - a. For the intermittent missing values, the missing values in each data set will be filled in using the MCMC method with multiple chain, monotone missing data imputing pattern, and non-informative prior for all parameters. Unless specified differently, the first 200 iterations will not be used (the “Burn-in” option). A total of 100 sets of imputations will be performed. The seed used for these imputations will be 762 and all other multiple imputation procedures described in this SAP will use this same seed as well. The resulting 100 imputed data sets will have a monotone missing pattern and will be imputed using a method for monotone missingness. Note that a separate imputation procedure must be invoked in SAS for each treatment group as the seed cannot be set for by groups beyond the first when using a by statement in PROC MI.
 - b. For monotone missing data, monotone regression will be used to impute missing data. A separate regression model is estimated for each variable with missing values (ie,

measurement at each time point). Based on the resulting model, a new regression model is then drawn and is used to impute the missing values for the variable. Since the data set has a monotone missing data pattern, the process is repeated sequentially for variables with missing values. This procedure will be based on the 100 imputed datasets generated from the MCMC procedure and will be performed by imputation. The SAS® PROC MI procedure will be used for the imputation.

In both cases, Hurley Stage at Baseline, Baseline antibiotic use, and value of the variable of interest at Baseline and at each post-Baseline visit (prior to the time point of interest) will be included in the imputation model. The post-Baseline values will need to be specified in chronological order in the imputation model so that SAS® PROC MI imputes variables from left to right (eg, the Week 2 value will be first imputed using regression based on the Baseline value, and then Week 4 value will be imputed using regression based on Baseline and Week 2 values, etc). The resulting data sets for each treatment arm will be combined into one complete data set based on each of the 100 imputations.

Note: The imputation model based on the MCMC method will only allow joint multivariate normal variables. Therefore, Hurley Stage at Baseline and Baseline antibiotic use will be re-coded as indicator variables. For Baseline antibiotic use, this will simply be 0 for Baseline antibiotic non-users and 1 for Baseline antibiotic users. For Hurley Stage at Baseline, this will be 0 for Hurley Stage II participants and 1 for Hurley Stage III participants. In order to achieve model convergence, Baseline antibiotic use may be dropped from the model. If convergence is still not obtained, then Hurley Stage at Baseline may also be dropped from the model. Additionally, if a variable is dropped in order to allow convergence for one model in a study, that variable does not have to be dropped from other models in the study if the model converges without dropping the variable. In other words, model convergence should be evaluated for each efficacy variable independently.

Note: The imputation of each lesion type (inflammatory nodule, abscess, draining tunnel, etc) will be performed separately. The 100 data sets obtained for each type will be merged by imputation number and subject number.

2. For each complete imputed data set, the dichotomous responder variable (eg, HiSCR 0 or 1) will be computed. Each complete imputed data set will then be analyzed based on the logistic regression model.

Note: For derivation of HiSCR response, the AN, inflammatory nodule, abscess, and draining tunnel (fistula/sinus tract) counts at Week 16 in the imputed data sets will be compared directly to the observed Baseline counts to determine response. If values outside of the pre-defined range of values for lesion count (<0) are imputed, they will be cut off as appropriate after the multiple imputation procedure but before deriving the responder variable. For example, an imputed draining tunnel (fistula/sinus tract) count of -1 would be changed to 0 before deriving the HiSCR responder variable. Additional ranges for values for secondary and other endpoints are defined in Table 4-2.

Note: Standard rounding rules will also be applied to the imputed values of endpoints that can only take integer values (eg, abscess count). For example, if a study participant has an abscess count imputed as 2.4, this imputed value would be rounded down to 2. This rounding step is performed after the multiple imputation but before deriving the responder variable.

Table 4–2: Imputation allowable ranges by variable

Variable	Minimum Value	Maximum Value	Integer Values Only
Lesion count ^a	0	--	Yes
DLQI total score	0	30	Yes
hs-CRP	LLOQ/2	--	No
HSSDD item score	0	10	No
HSSQ item score	0	10	Yes
HiSQOL symptom status score	0	16	Yes
HiSQOL psychosocial impact score	0	20	Yes
HiSQOL impact on physical activities score	0	32	Yes
EQ-5D-3L VAS	0	100	Yes
WPAI dimension scores	0	100	No for variables: “Percent work time missed due to problem” and “Percent overall work impairment due to problem”. Yes for variables: “Percent impairment while working due to problem” and “Percent activity impairment due to problem”. These two variables can only take values that are multiples of 10.

^a Lesion counts will be imputed separately for each lesion type (abscesses, draining tunnels [fistulas/sinus tracts], inflammatory nodules, non-draining tunnels [fistulas/sinus tracts], non-inflammatory nodules, HS scars). The imputed lesion counts will be used to derive the endpoints that are dependent on the lesion count data (eg, HiSCR₅₀).

- Estimates of the adjusted responder rate for each treatment group and the associated SE are obtained from the logistic regression of each of the 100 imputed data sets. These estimates will be combined for overall inference using Rubin’s rules, which account for the uncertainty associated with the imputed values (Rubin, 1987), and the combined estimates and SEs will be used to construct 95% CIs using the logit scale. This will be done using SAS PROC MIANALYZE. The combined estimates and 95% CIs on the logit scale will be back-transformed using the inverse logit link function to obtain the adjusted responder rates (%) and associated 95% CIs.

Note: The (unadjusted) proportion of responders will be calculated at each time point by treatment group from the imputed datasets using SAS PROC FREQ. These results will also be combined into an overall inference using SAS PROC MIANALYZE.

Some key points to consider relative to the calculation of the odds ratios and corresponding confidence intervals are noted below:

As the estimates of the odds ratios from the logistic regression models in Step 3 follow a log-normal distribution, a log transformation is needed to normalize these 100 odds ratio estimates. That is because the procedures for combining results from multiple imputed datasets assume that the statistics estimated from each imputed dataset are normally distributed. Therefore, the log of the odds ratio estimates from the logistic regression model are used when combining into a single inference (Step 3). Additionally, the SE for the odds ratios are transformed as follows:

$$SE = \frac{\log(UCL) - \log(LCL)}{2Z_{\alpha/2}}$$

Where UCL and LCL are the upper and lower confidence limit, respectively, for the CI of the odds ratio from the logistic regression model, and $Z_{\alpha/2}$ is the relevant critical value from the standard normal distribution (2.24 for a 97.5% CI). The estimates of the log odds ratio for Bimekizumab relative to placebo and the corresponding upper and lower CLs will be provided. The odds ratio will be then estimated by exponentiating the estimate of the log odds ratio. The odds ratio and the confidence limits of the odds ratio will be estimated as follows:

$$OR = \exp(\text{Log odds ratio estimate})$$

$$LCL = OR * \exp(-SE * Z_{\alpha/2})$$

$$UCL = OR * \exp(SE * Z_{\alpha/2})$$

Where OR is the back-transformed estimate of the odds ratio just described, SE is the SE of the log odds ratio and $Z_{\alpha/2}$ is the relevant critical value from the standard normal distribution (2.24 for a 97.5% CI). These calculations will be done such that odds ratios and corresponding CIs are calculated for the odds ratio of bimekizumab vs. placebo.

Note: If one dose regimen is tested at the 0.05 significance level as determined in Section 4.5, then the confidence interval will be 95% instead of 97.5% for that dose with a corresponding $Z_{\alpha/2}$ of 1.96.

In addition to calculating the odds ratio, associated CIs, and p-values for the pairwise comparisons of bimekizumab and placebo, the estimated proportion of responders (ie, estimated responder rate) and the difference in the proportion of responders between each bimekizumab treatment group and placebo will be estimated, and 2-sided 95% CIs will be created for each difference. The creation of the estimates of the differences will be completed for each bimekizumab treatment group using the process detailed below:

1. Use the logistic regression model to calculate:

Least squares mean estimates of the log odds of bimekizumab (G_B) and placebo (G_P), as well as their corresponding standard errors (S_B and S_P , respectively).

Standard error of the least squares mean estimate of the log odds ratio (S_R)

2. Compute estimates for predicted proportions using the following transformations:

$$P_B = \exp(G_B)/(1 + \exp(G_B))$$

$$P_P = \exp(G_P)/(1 + \exp(G_P))$$

The difference in proportions is then given by:

$$D = P_B - P_P$$

3. Estimate the standard error of D by:

$$S_D = \text{sqrt}[P_B^2(1-P_B)^2S_B^2 + P_P^2(1-P_P)^2S_P^2 + P_B(1-P_B)P_P(1-P_P)S_R^2 - P_B(1-P_B)P_P(1-P_P)(S_B^2 + S_P^2)]$$

The MCMC method for multiple imputation, as previously outlined, will be used to account for missing values. The calculation steps described above will be based on the results provided from the logistic regression model of the multiple imputed datasets. An estimate for the difference in proportions, D, and corresponding standard error, SD, will be computed for each of these datasets. The results from these analyses will be combined into a single estimate of the difference in predicted proportion of response and a 2-sided 95% CI interval using SAS PROC MIANALYZE.

Note that this procedure indicates that the imputation model will be applied for each treatment group separately in PROC MI, which will be the default method. However, in the event there are computational challenges with the imputation model (eg, due to a standard deviation of 0 for responses of a given imputation), it is acceptable to modify the imputation model to include treatment as a variable in the model rather than running a separate model for each treatment group. It should be noted that doing so assumes that treatment does not interact with any of the other variables in the imputation model.

Continuous endpoint

For continuous endpoints (eg, Change from Baseline in DLQI total score at Week 16), the MI method will be applied as follows:

1. The MCMC/monotone regression method described above in Step 1 for binary endpoints will be performed.
2. Based on the multiply imputed data sets obtained for the given variable, the change from Baseline will be derived for each of the 100 complete imputed data sets based on the observed Baseline value and the observed/imputed post-Baseline values. Note that if the value itself is being summarized, no additional derivation is needed.
3. If a statistical model is being used for the analysis of the variable, then that will be performed for each imputation in this step. If no statistical model is being used, then simple descriptive statistics will be calculated.
4. For data excluding hs-CRP, the following rules apply. The results of the 100 imputed data sets (based on the statistical model or descriptive statistics) are combined with means and standard errors calculated using Rubin's rules (via PROC MIANALYZE). Note that for the calculation of other descriptive statistics such as the median, min, and max, Rubin's rules do not apply. MI estimates will be computed by simply averaging the estimates from the multiple repetitions of the imputation algorithm. Thus, for median, Q1, Q3, minimum and maximum, the following approach will apply:

- The data will be summarized by treatment, visit, and imputation, and the summary statistics will be computed.
- Results will be summarized by taking the mean value of each summary statistic at each visit across all imputations.
- The number of decimal places will remain the same as the original for display purposes (ie, if the mean was presented to 1 decimal place, then the mean of the means will also be presented to 1 decimal place).

For hs-CRP only, the following rules apply. The hs-CRP data will be presented using the geometric mean, 95% CI for the geometric mean, median, Q1, Q3, minimum and maximum. The change from Baseline will be expressed as the ratio to Baseline in the summaries. The following approach will be applied:

- Following the MI procedure, the ratio to Baseline will be calculated for any of the imputed values
- The natural logarithm of the absolute values and of the ratios to Baseline will be calculated
- The logged values will be summarized (using PROC MEANS) by treatment, visit and imputation
- The datasets will be combined using PROC MIANALYZE in order to get the mean and 95% CI estimates from the absolute values and ratios to Baseline (based on logged data) across imputations
- The estimates of the mean and 95% CI will be back-transformed to obtain the geometric mean and 95% CI on the original scale
- For the median, Q1, Q3, minimum and maximum the procedure outlined above for the other endpoints will be followed

If the imputation model cannot converge, LOCF will be used.

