2.4 Determination of sample size

A total of 490 study participants will be randomly assigned in a 2:2:2:1 ratio (stratified by Hurley Stage and current antibiotic use) to the following treatment arms:

- Bimekizumab ██████████ during Initial Treatment Period (Weeks 0-16) and Maintenance Treatment (Weeks 16-48) Period, N=140
- Bimekizumab ██████████ during Initial Treatment Period (Weeks 0-16), and Bimekizumab ██████████ during Maintenance Treatment Period (Weeks 16-48), N=140
- Bimekizumab ██████████ during Initial Treatment (Weeks 0-16) and Maintenance Treatment Periods (Weeks 16-48), N=140
- Placebo during Initial Treatment Period (Weeks 0-16), and Bimekizumab ██████████ during Maintenance Treatment Period (Weeks 16-48), N=70

The analysis of the primary efficacy endpoint and secondary efficacy endpoints are based on a comparison of bimekizumab versus placebo at Week 16, with alpha adjustment strategy as indicated in Section 4.5.

The power to detect a statistically significant difference for each of the endpoints are shown in Table 2-1. Notably, with a 2-sided significance level of 0.025, the sample size of 140:70 provides 73% power for detecting at least a difference of 1.5 (bimekizumab ██████████ vs placebo) for the Worst Skin Pain change from Baseline (CFB) endpoint.

Given the high level of power for each of the primary and key secondary endpoints at the 0.025 significance level for the ██████████ comparison (power \geq 0.89), and per the alpha spending strategy, there is a high likelihood that the ██████████ comparison of Worst Skin Pain CFB vs placebo will be allowed to be tested against the 0.05 level of significance. The power for this latter test is 81%. The sample size is thus ultimately driven by the Worst Skin Pain CFB endpoint.

Furthermore, the randomization ratio of 2:2:2:1 has been chosen to provide study participants with a high probability (6/7 ~ 86%) of being randomized to active study drug.

After randomization for this study was complete, an additional endpoint to assess Worst Skin Pain response was included in the sequential testing procedure. This additional endpoint is based on the threshold for clinically meaningful change and is defined as at least a 3 point decrease from Baseline in HSSDD weekly worst skin pain score at Week 16 among study participants with a score of \geq 3 at Baseline. Note that the power calculations reported in Table 2-1 for this

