4.5 Multiple comparisons/multiplicity

To control the overall type I error rate at 0.05 for the multiple comparisons in the primary and secondary efficacy endpoints, a closed testing procedure under a parallel gatekeeping framework will be applied (Sun, 2018).

[figure not shown]
Under this framework, each bimekizumab dose of [REDACTED] and [REDACTED] will be compared to placebo in the first instance at a familywise error rate of 0.025 ($\alpha/2$). Simultaneously within each dose, closed testing for the primary and secondary efficacy endpoints will be performed as follows:

1. Step 1: Test HiSCR₅₀ at significance level 0.025.
2. Steps 2 to 6 – If Step 1 is significant at 0.025 then test each secondary endpoint sequentially in the order shown in Figure 4-1, moving to the next step only if significance achieved at 0.025.
3. In the event that Step 6 is significant at 0.025 for a given dose, then Steps 1 to 6 will be repeated for the other dose using a significance level of 0.05.

The secondary efficacy variables supporting the primary efficacy variable are listed below, and will be included in the multiplicity adjustment using the analysis methods specified in Section 8.3:

1. Proportion of study participants who achieve HiSCR₇₅ at Week 16.
 - a. bimekizumab [REDACTED] vs placebo
 - b. bimekizumab [REDACTED] vs placebo
2. Proportion of study participants who experience at least 1 flare by Week 16, with flare defined as a $\geq 25\%$ increase in AN count with an absolute increase in AN count of ≥ 2 relative to Baseline.
 - a. bimekizumab [REDACTED] vs placebo
 - b. bimekizumab [REDACTED] vs placebo
3. Absolute CFB in DLQI Total Score at Week 16.
 - a. bimekizumab [REDACTED] vs placebo
 - b. bimekizumab [REDACTED] vs placebo
4. Absolute CFB in Skin Pain Score at Week 16, as assessed by the “worst skin pain” item (11-point numeric rating scale) in the HSSDD.
 - a. bimekizumab [REDACTED] vs placebo
 - b. bimekizumab [REDACTED] vs placebo
5. Skin pain response at Week 16, based on the threshold for clinically meaningful change (defined as at least a 3 point decrease from Baseline in HSSDD weekly worst skin pain score) at Week 16 among study participants with a score of ≥ 3 at Baseline.
 - a. bimekizumab [REDACTED] vs placebo
 - b. bimekizumab [REDACTED] vs placebo

Figure 4-1: Sequence of testing

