8.2.2 Primary analysis of the primary efficacy endpoint

The primary endpoint is the HiSCR₅₀ response at Week 16 and corresponding analyses are based on the RS. The primary efficacy analysis will evaluate the composite estimand in the RS as described in Table 8–1. The composite estimand combines the clinically meaningful improvement from Baseline based on the HiSCR₅₀ response and completion of study treatment through Week 16 without receiving systemic antibiotic rescue medication or discontinuing IMP due to an AE or lack of efficacy.

The following 4 attributes describe the estimand that will be used to define the treatment effect of interest for the primary efficacy analysis:

1. Population=Study participants meeting the protocol-specified inclusion/exclusion criteria.
2. Study participant-level outcome=HiSCR₅₀ at Week 16.
3. Intercurrent event handling=An intercurrent event is defined as receipt of systemic antibiotic rescue medication or discontinuation of study treatment due to an AE or lack of efficacy prior to Week 16. More information is provided in Section 3.9. A composite strategy will be implemented in which a positive clinical outcome is defined as achieving HiSCR₅₀ at Week 16 and not receiving systemic antibiotic rescue medication, and not discontinuing study treatment due to an AE or lack of efficacy through Week 16. Any missing data at Week 16 that are not preceded by an intercurrent event will be imputed using multiple imputation as defined in Section 4.2.1. The rationale for this composite estimand is provided in Section 4.2.3.1.

4. Population-level summary measure=conditional odds ratio comparing bimekizumab to placebo adjusted for stratification factors used in the randomization.

The statistical hypothesis for the HiSCR₅₀ response at Week 16 is that the conditional odds ratio for the HiSCR₅₀ response in the bimekizumab treatment group relative to the placebo group is equal to 1.

The primary analysis will be based on a logistic regression model including a fixed effect for treatment, Hurley stage at Baseline, and Baseline antibiotic use. The odds ratio versus placebo, p-value (from Wald test), and 97.5% CI will be calculated. If one dose regimen is tested at the 0.05 significance level as determined in Section 4.5, then the confidence interval will be 95% instead of 97.5% for that dose with a corresponding $Z_{\alpha/2}$ of 1.96.

The number and percentage of participants who are HiSCR₅₀ responders at Week 16 will be summarized.

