21-30 = extremely large effect on patient’s life

This categorization will not be utilized in the analysis.

Because Q7 has a sub-question (referred to as Q7a here) after the leading yes/no question, some clarifying rules for scoring are provided:

- If Q7 is marked as “yes”, a score of 3 is given regardless of the responses to Q7a.
- If Q7 is marked as “no”, “not relevant”, or is missing and Q7a is “A lot”, a score of 2 is given.
- If Q7 is marked as “no”, “not relevant”, or is missing and Q7a is “A little”, a score of 1 is given.
- If Q7 is marked as “no”, “not relevant”, or is missing and Q7a is “Not at all”, a score of 0 is given.
- If Q7 is marked as “no” or “not relevant” and Q7a is missing, a score of 0 is given.
- If Q7 is missing and Q7a is missing, Q7 is considered unanswered (see below for details on how this impacts the DLQI total score).

If 1 question is left unanswered, this is scored 0 and the scores are summed and expressed as usual out of a maximum of 30. If 2 or more questions are left unanswered, the questionnaire is not scored.

Change from Baseline in DLQI total score is defined as Week 16 DLQI total score minus Baseline DLQI total score.

8.3.3.1 Primary analysis of change from Baseline in DLQI Total score at Week 16

Missing data imputation described in Section 4.2.1.2 will be applied.

Change from Baseline in DLQI total score will be presented by treatment group. The analysis model will be based on an ANCOVA with fixed effects of treatment, Hurley Stage at Baseline, Baseline antibiotic use and Baseline value as a covariate. The least square mean (LSM), standard error (SE), and 95% CI for the LSM will be presented by treatment group. For the comparison between placebo and bimekizumab: the difference between the LSM, the associated 97.5% CI for the contrasts, and the corresponding p-value will be presented. If one dose regimen is tested at the 0.05 significance level as determined in Section 4.5, then the confidence interval will be 95% instead of 97.5% for that dose with a corresponding $Z_{\alpha/2}$ of 1.96. Estimand and intercurrent event details are specified in Table 8–2.

8.3.3.2 Sensitivity analysis of change from Baseline in DLQI Total score at Week 16

A sensitivity analysis using the same analysis model as in Section 8.3.3.1 will be used, based on observed data. Estimand and intercurrent event details are specified in Table 8–2.

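### The confidence interval for the difference in responder proportions is fixed at 95%, although the same comparison is tested at two-sided 0.025 and its odds ratio carries a 97.5% interval

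*SAP*

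**What the plan says.** Section 4.5 starts each dose's sequence at the split level: "Step 1: Test HiSCR₅₀ at significance level 0.025". A dose moves to 0.05 only when the other dose has passed Step 6 at 0.025. Section 2.4 confirms that this level is two-sided: "with a 2-sided significance level of 0.025, the sample size of 140:70".

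The intervals for the tested effect measures follow that rule:

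- **Primary odds ratio (8.2.2):** "The odds ratio versus placebo, p-value (from Wald test), and 97.5% CI will be calculated". Section 4.2.2.1 gives the multiplier, which "is the relevant critical value from the standard normal distribution (2.24 for a 97.5% CI"). For a dose tested at 0.05, "then the confidence interval will be 95% instead of 97.5% for that dose with a corresponding" multiplier of 1.96.
- **Continuous secondaries (8.3.3.1 and 8.3.4.1):** the LS-mean difference is reported with "the associated 97.5% CI for the contrasts", and the same switch applies.
- **Skin pain response odds ratio (8.3.5.1):** 97.5%, with the same switch.

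The difference in responder proportions does not follow it. It comes from the same logistic model and the same pairwise comparison. Section 4.2.2.1 states that "2-sided 95% CIs will be created for each difference", and repeats 95% where the estimates are combined over imputations. The note on switching levels stands before this text, among the odds ratio calculations, and nothing in the section calls the difference interval descriptive.

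**The concern.** One comparison carries two confidence levels. For a dose held at 0.025, the difference interval is narrower than its test level warrants. If p falls between 0.025 and 0.05, the comparison fails and that dose's sequence stops, yet the difference interval will usually exclude zero. A reader who takes the interval as the result would see an effect that the multiplicity procedure did not grant.

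The method in Section 4.2.2.1 is written for binary endpoints in general, so the mismatch reaches HiSCR75, flare and skin pain response as well as HiSCR50. The SAP matches interval to test level for the continuous between-arm differences and gives no reason for treating the binary differences otherwise.

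**Working it through.** **Inputs.** Two-sided 0.025 per dose (2.4, 4.5). Allocation 140:140:140:70, with two arms pooled to 280 at Week 16 (2.4). From Table 2-1: HiSCR50 rates 0.60 (N=280), 0.50 (N=140) and 0.25 (placebo, N=70); skin pain response 0.43 against 0.23 with 104:52. The tables below have no covariates and no imputation.

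**Step 1: the plan's own figures.** The normal quantile for two-sided 0.025 is 2.2414 (plan: 2.24). Pooled-variance power for 0.50 against 0.25, 140:70:

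- pooled rate = (70 + 17.5)/210 = 0.4167
- SE under the null = √[0.4167 × 0.5833 × (1/140 + 1/70)] = 0.0722
- SE under the alternative = √[0.25/140 + 0.1875/70] = 0.0668
- power = Φ[(0.25 − 2.2414 × 0.0722)/0.0668] = Φ(1.32) = 0.907 (plan: 0.90)

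The pooled regimen gives 0.9996 (plan: 0.99). So two-sided 0.025 is the planning level.

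**Step 2: one comparison, two levels.** Take 56/140 against 18/70.

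- log OR = ln[(56/84)/(18/52)] = 0.655; SE = √(1/56 + 1/84 + 1/18 + 1/52) = 0.323
- z = 2.03, p = 0.043, so the test fails at 0.025
- OR = 1.93; 97.5% CI = exp(0.655 ± 2.2414 × 0.323) = 0.93 to 3.98

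In the SAP's formula for the standard error of the difference, the last two terms cancel without covariates, because the log odds ratio variance is then the sum of the two arm variances. This leaves √[0.400 × 0.600/140 + 0.257 × 0.743/70] = 0.0667.

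| Difference 14.3 points | Interval (points) | Excludes 0? |
|---|---|---|
| 95% (as planned) | 1.2 to 27.4 | yes |
| 97.5% (test level) | −0.7 to 29.2 | no |

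The pooled regimen behaves alike: 110/280 against 18/70 gives p = 0.037, OR 97.5% CI 0.96 to 3.66, and a difference of 13.6 points with 95% CI 1.8 to 25.3. In every table checked with p from 0.025 to below 0.05 (14, 18, 20 or 21 placebo responders of 70), the 95% difference interval excluded zero.

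**Step 3: frequency for a dose held at 0.025.** Exact binomial enumeration of a failed test at 0.025 with a difference interval above zero:

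| True rates | 95% CI | 97.5% CI |
|---|---|---|
| HiSCR50 0.50 v 0.25 (140:70) | 4.8% | 1.5% |
| HiSCR50 0.40 v 0.25 (140:70; 0.40 is an assumption) | 16.5% | 6.2% |
| Skin pain response 0.43 v 0.23 (104:52) | 15.9% | 6.8% |

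For the pooled regimen at 0.60 against 0.25, the figure with a 95% interval is about 0.05%.

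**Step 4: allow for alpha release.** Step 3 ignores whether the single-arm regimen is still at 0.025. I simulated normal test statistics with means set to the Table 2-1 powers. The correlation between doses from the shared placebo arm is √(140/210) × √(280/350) = 0.73. The correlation between endpoints is not in the SAP and was varied from 0 to 0.8. The pooled regimen fails some step in about 12 to 19% of trials. The chance that the single-arm regimen both stays at 0.025 and has p between 0.025 and 0.05 is about 0.6 to 1.4% for HiSCR50 and 1.0 to 1.7% for skin pain response. The latter does not require that regimen to have reached Step 6.

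**Step 5: cost in width.** 2.2414/1.9600 = 1.14.

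**The case against.** The strongest reply is that no decision uses this interval. The declared summary measure is the conditional odds ratio, tested by a Wald p-value within the sequence in 4.5, and 4.2.2.1 offers the difference as an addition. A pattern can also be read into the levels: the measure that carries the test follows alpha, while accompanying estimates (adjusted responder rates, group LS means, subgroup differences in 4.8) get 95%. The first part stands in full. The second is plausible, but the SAP does not state the convention, and it leaves an unlabelled between-arm contrast on the primary endpoint at a level different from its test.

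Two stronger readings are tempting, and the documents support neither.

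- A reader might infer that the family-wise error is inflated. With no effect, at least one of two 95% difference intervals would exclude zero in 8.2% of trials, against 4.2% at 97.5%. That is not an error rate of this plan, because nothing is claimed from these intervals.
- A reader might take the whole chance of p between 0.025 and 0.05 as the size of the problem: about 4 points for HiSCR50 (power 0.907 at 0.025, 0.948 at 0.05) and 12 points for skin pain response (53% and 65% in Section 2.4). Those figures ignore alpha release and overstate it several-fold at the planned effects.

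Two limits on the remedy also stand. Matching levels does not remove all discordance, because the test is on the log-odds scale: 57/140 against 18/70 has p = 0.034, yet its 97.5% difference interval, 0.04 to 30.0 points, still just excludes zero. And since testing stops at the first failure, an interval that excludes the null at a later step never replaces the sequential decision, at any level. Finally, 8.2.2 lists only the odds ratio, p-value and 97.5% CI, so it is an assumption that the difference will be tabulated alongside them.

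**Conclusion.** The inconsistency is real and confined to reporting. Section 4.2.2.1 fixes the proportion difference at 95% while the odds ratio for the same comparison, and the LS-mean differences of the continuous secondaries, follow the test level. The primary test, its type I error, the power and the estimand are unaffected.

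It matters only for a dose held at 0.025 with p roughly between 0.025 and 0.05. At the planned effects that is about 1% of trials for HiSCR50 and for skin pain response. This rests on the Table 2-1 powers, an assumed range of endpoint correlation, and tables without covariates or imputation. It would be more frequent with smaller true effects: given a dose held at 0.025, 16.5% instead of 4.8% if the HiSCR50 rate were 0.40 rather than 0.50. It is worth correcting because the SAP already contains the rule that resolves it.

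**What to change.** In both places in Section 4.2.2.1 where the difference in proportions is given a 95% interval, state that for the confirmatory Week 16 binary endpoints (HiSCR50, HiSCR75, flare, skin pain response) the interval is two-sided 97.5%, or 95% for a dose tested at 0.05 under Section 4.5. By-visit and subgroup difference intervals (4.8) can stay at 95%, labelled as descriptive and not adjusted for multiplicity, so that the two levels are not read as equivalent.

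The cost is one wording change and one alpha setting in the combining step, with difference intervals about 14% wider for a dose held at 0.025. Labelling every difference interval as descriptive would be cheaper and change no number, but it would leave two levels on one comparison. Either way, add a sentence that significance is read only from the sequence in 4.5 and not from whether an interval excludes the null.
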